4.3.2 OPEN/IWRS User Requirements

OPEN/IWRS users must meet the following requirements:

- Have a valid CTEP-IAM account (*i.e.*, CTEP username and password).
- To enroll patients or request slot reservations: Be on an ETCTN Corresponding or Participating Organization roster with the role of Registrar. **Registrars must hold a minimum of an AP registration type.**
 - To approve slot reservations or access cohort management: Be identified to Theradex as the "Client Admin" for the studySlot enrollment will be used for the first 10 patients in each arm for the colorectal cancer cohort to allow for the parallel Simon two-stage designs. For the NSCLC cohorts, slot enrollment will be used for the first 20 patient in each arm to allow for an early safety look after 10 patients per arm, and for an interim evaluation of efficacy at 20 patients per arm.
- Have regulatory approval for the conduct of the study at their site.

Prior to accessing OPEN/IWRS, site staff should verify the following:

- All eligibility criteria have been met within the protocol stated timeframes.
- If applicable, all patients have signed an appropriate consent form and HIPAA

authorization form.

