 - o Note: Patients enrolled on Arm B should continue to receive lower dose radiation (2 Gy delivered in 4 fractions) with each of the first 4 cycles of treatment (weeks 2, 6, 10, 14). The radiation target and treatment plan need not change between treatment courses; however, if there is clinical or radiographic evidence of complete resolution of the irradiated lesion, this lesion should not be treated with additional radiation. If this occurs and there is another lesion appropriate for palliative radiation that satisfies the above criteria, additional lower dose radiation may be considered after discussion with the study PI. This irradiation of a new lesion will not be counted as tumor progression.

5) Dosimetry:

- a. Only photons treatments are allowed, and volumetric treatment planning is mandated.
- b. Planning may include 3D conformal, IMRT or SBRT, as appropriate to each individual case / lesion to achieve coverage of the PTV target and maintain normal tissue tolerance. IROC credentialing is required for the most complex modality (IMRT>3D) used by each center as well as for IGRT (see section 4.2.2).
- c. PTV coverage should ideally be 95% of PTV conformally covered by the prescription isodose surface (D95=100%), , while maintaining normal tissue dose constraints as indicated below. Bolus may be used as appropriate
- d. The percentage PTV covered to 100% of the prescription dose will be reported along with the maximum hotspot;
- e. Doses higher than the prescription isodose (i.e., hotspots) should be manipulated to occur within the planning target volume.
- f. Note:For patients prescribed 24 Gy in 3 fractions, maximum hotspot should not exceed 115% in any case.
- g. For purposes of dose planning and calculation of monitor units for actual treatment, this protocol requires tissue density heterogeneity corrections approved by IROC. Examples of appropriate tissue density heterogeneity correction algorithms include properly commissioned superposition/convolution (collapsed cone), AAA, and Monte Carlo. Simple pencil beam and Clarkson algorithms that account for attenuation but not scatter will not be allowed.
- h. For 3D conformal cases, coplanar or non-coplanar beam arrangements will be custom designed for each case to deliver conformal prescription dose distributions.
- i. For IMRT cases, the treatment dose plan may be made up of multiple static beams or arcs, and the apertures are determined by inverse treatment planning

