5.2 Definition of Dose-Limiting Toxicity

Although there is significant safety data for the MEDI4736/ tremelimumab treatment and palliative radiation, the combination is relatively untested, although emerging safety data suggests the combination of the two treatments (specifically in regards to limited palliative radiation treatment fields) do not increase the rates of irAE or radiation toxicity [64]. Although this retrospective data compares favorably to previous studies testing combined checkpoint inhibition, to provide greater confidence in the safety of radiation and combined checkpoint inhibition, DLT's will be monitored in a step-wise fashion and over time. As part of the safety assessment for the NSCLC cohort, complete review of the adverse event data for the first 10 patients assigned to MEDI4736(durvalumab)/tremelimumab/high-dose RT and for the first 10 patients assigned to treatment with MEDI4736(durvalumab)/tremelimumab/low-dose RT will occur after completion of two cycles of therapy. If three or more patients within a therapy arm experience one or more pre-specified dose-limiting toxicities the addition of RT will be considered too toxic and enrollment to that arm will stop. If this occurs in the high-dose radiation arm, all safety data from that arm will be reviewed and a protocol amendment may be considered.

Concurrent with the end of the first stage of each Simon design for the colorectal cohort, a complete safety review of adverse event data will be conducted for each treatment. If three of more patients within a therapy experience one or more pre-specified dose-limiting toxicities, enrollment to that arm will stop.

Dose-limiting toxicity (DLT) is based on the CTEP Active Version of the NCI Common Terminology Criteria for Adverse Events (CTCAE). Although we will continue to monitor toxicity over time, the DLT period in this study refers to toxicities experienced during the first 4 weeks of treatment.

DLTs will be graded according to the National Cancer Institute's CTCAE v5.0 https://ctep.cancer.gov/protocolDevelopment/electronic_applications/ctc.htm (<http://ctep.cancer.gov/forms/CTCAEv45.pdf>).

A DLT will be defined as any <<Grade 3 or higher>> toxicity that occurs during the DLT evaluation period. Toxicity that is clearly and directly related to the primary disease or to another etiology is excluded from this definition. The following will be DLTs:

- Any Grade 4 irAE
- Any \geq Grade 3 colitis

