will stop early for futility. Under this design, the probability of stopping for futility at the ^[1]_[SEP] interim analysis is 0.56 if the null hypothesis is true. Sample size and power calculations were conducted using EaST 5.4. Note that enrollment to the MEDI4736(durvalumab)/tremelimumab-alone arm will continue as long as enrollment continues in at least one RT arm.

Colorectal Cancer: Best overall response rate is the endpoint on which the sample size is based for cohort 2. There is a low historical response rate in microsatellite stable colorectal cancer [14]; therefore, we will employ two, parallel, Simon optimal two-stage designs to identify therapy combinations worthy of further study in this patient population. A promising response rate in this population would be 20%. Sixty patients will be randomly assigned to high-dose or low-dose radiotherapy plus MEDI4736(durvalumab)/tremelimumab (30 per therapy). The high-dose and low-dose designs will be conducted separately. Ten patients will be enrolled in the first stage for each therapy. If there is at least one response among the first ten patients, then an additional 20 patients will be enrolled to that treatment arm for a total of 30 patients in each comparison. If four or more patients in a comparison have response then that treatment combination would be considered promising. Each design has a type-I error of 5% (target alpha=0.10) and 80% power to detect a difference between a null rate of 5% and a promising response rate of 20%. If the null hypothesis is true, the probability is 0.60 that accrual in that treatment arm will stop at the end of the first stage. If the cohort combining LDFRT is stopped early for futility, we will review the data and possibly amend the protocol at that time.

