13.6 Interim Safety Analysis

NSCLC: For an early and detailed safety assessment, complete review of the adverse event data for the first 10 patients assigned to MEDI4736(durvalumab)/tremelimumab/high-dose RT and for the first 10 patients assigned to treatment with MEDI4736(durvalumab)/tremelimumab/low-dose RT will occur after completion of one cycle (4 weeks) of therapy. If three or more patients within a therapy arm experience one or more dose-limiting toxicities, the addition of RT will be considered too toxic and enrollment to that arm will stop.

Colorectal Cancer: Concurrent with the end of the first stage of each Simon design, a complete safety review of adverse event data will be conducted for each treatment after completion of two cycles of therapy. If three or more patients within a therapy experience one or more severe or pre-specified dose-limiting toxicities, enrollment to that arm will stop.

The table below summarizes the probability of observing three or more severe or unexpected toxicities in the first 10 patients of a cohort for various underlying true probabilities. If the true incidence of severe or unexpected toxicities is 25% or higher, then the probability is at least 0.47 that three or more patients will be observed with these toxicities at the time of the early safety monitoring.

True Incidence of Unexpected or Severe Toxicity	Probability of Observing Three or More Patients with Toxicity among First 10
10%	0.07
15%	0.18
20%	0.33
25%	0.47
30%	0.62

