13.8 Analysis of Secondary Endpoints

13.8.1 Safety

Assessments of safety and tolerability will be performed on an ongoing basis. At the conclusion of the study, safety data will be summarized for each treatment arm within each cohort. The proportions of subjects with grade-3 or higher adverse events will be presented with exact binomial confidence intervals. Although it is unexpected after a successful early safety assessment, if at any time after the early safety review 33% or more of patients in a cohort are observed with severe toxicities, the regimen in that cohort will pause and a comprehensive safety analysis will be conducted.

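### At 3 DLTs in the first 10 NSCLC low-dose RT patients, adding RT is judged too toxic but only enrolment stops; no arm-level decision is specified on the RT courses still due to patients on that arm

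*Combined protocol and SAP*

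**What the plan says.** **The rule.** Sections 5.2 and 13.6 provide a full adverse event review of the first 10 NSCLC patients in each RT arm, after two cycles according to 5.2 and after one cycle (4 weeks) according to 13.6. If three or more patients in an arm have a DLT, "the addition of RT will be considered too toxic and enrollment to that arm will stop".

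**The next step.** Section 5.2 adds one, for one arm: "If this occurs in the high-dose radiation arm, all safety data from that arm will be reviewed and a protocol amendment may be considered". For low-dose RT, the only comparable sentence is in 13.4.1, for the colorectal cohort and a futility stop: "If the cohort combining LDFRT is stopped early for futility, we will review the data and possibly amend the protocol at that time".

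**The RT schedule.** Arm A receives one course starting in week 2. For Arm B, 5.1 (item 4, timing) says: "Patients enrolled on Arm B should continue to receive lower dose radiation" with each of the first four cycles, in weeks 2, 6, 10 and 14. The exception given there is "complete resolution of the irradiated lesion, this lesion should not be treated with additional radiation".

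**The later pause.** Section 13.8.1 sets a further threshold, introduced in these words: "Although it is unexpected after a successful early safety assessment, if at any time after the early safety review 33% or more of patients". What it counts is severe toxicities, per cohort. Once the threshold is reached, "the regimen in that cohort will pause and a comprehensive safety analysis will be conducted".

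**Patient-level rules.** Section 6 holds RT when a patient's own adverse event or drug hold requires it, and postpones missed courses rather than dropping them. It also takes a patient off treatment if drug or RT is permanently stopped for toxicity. Section 5.4 lists progression, illness, withdrawal, investigator judgment and sponsor termination, among others.

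**Colorectal cohort.** The 13.6 rule there also stops enrolment at three of 10, without the judgment that RT is too toxic. It too is silent on Arm B courses still due.

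**The concern.** The rule reaches a conclusion about a treatment component, but its only consequence is for patients not yet enrolled. Arm B is the arm where that matters, because its RT is repeated. An Arm B patient with no treatment-ending event of their own would, by default, receive further 2 Gy courses after the protocol has judged added RT too toxic. No one is assigned the decision on whether those courses go ahead. The all-data review that could supply the decision is attached to the arm whose RT is normally complete.

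A site that wanted to stop RT on the arm-level signal would meet a second difficulty. The off-treatment provision in Section 6 could be read as requiring it to withdraw durvalumab and tremelimumab as well. What is at stake is the safety of a small number of patients. No endpoint, error rate or estimate is affected.

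**Working it through.** **1. How often the rule fires.** Inputs: n = 10, trigger at 3 (13.6). P(X ≥ 3) = 1 − Σ(k = 0 to 2) C(10,k) p^k (1−p)^(10−k), and P(X = 3) = 120 p³ (1−p)⁷.

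| True rate p | Plan's figure | P(X ≥ 3) | P(X = 3) | Share of firings at exactly 3 |
|---|---|---|---|---|
| 10% | 0.07 | 0.070 | 0.057 | 0.82 |
| 15% | 0.18 | 0.180 | 0.130 | 0.72 |
| 20% | 0.33 | 0.322 | 0.201 | 0.62 |
| 25% | 0.47 | 0.474 | 0.250 | 0.53 |
| 30% | 0.62 | 0.617 | 0.267 | 0.43 |

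The plan's table reproduces. The 20% row rounds to 0.32 rather than 0.33, which is immaterial.

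**2. Does the 33% pause take over?** Read per arm and on DLTs alone, 3/10 = 30% is below 33% and 4/10 = 40% is above it. The last column therefore shows how often a firing would miss the pause. It is an upper bound, because severe events that are not DLTs can raise the count.

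If cohort means the three NSCLC arms pooled (10 each, an assumption), 10 of 30 are needed. Given that Arm B has fired, the probability is Σ(b = 3 to 10) P(B = b) P(Bin(20,q) ≥ 10 − b) / P(B ≥ 3). For Arm B rates of 20% to 40% and rates q of 10% to 25% in the other arms, it runs from 0.01 to 0.48.

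**3. Courses outstanding among the first 10.** Section 13.5 projects 6 NSCLC patients per month, so 2 per arm per month, one every (52/12)/2 = 2.17 weeks. Assume even accrual, treatment starting at registration, an immediate review, and courses 1, 5, 9 and 13 weeks after start. Counting back from the tenth patient:

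| Review | Weeks since start, newest first | Courses still due | Total |
|---|---|---|---|
| 4 weeks (13.6) | 4.0, 6.2, 8.3, 10.5, 12.7, 14.8 | 3, 2, 2, 1, 1, 0 | 5 patients, 9 courses |
| 8 weeks (5.2) | 8.0, 10.2, 12.3, 14.5 | 2, 1, 1, 0 | 3 patients, 4 courses |

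Placing courses at 2, 6, 10 and 14 weeks gives the same totals.

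**4. What lowers the count.** If the three DLT patients are off treatment and are a random three of the 10, the means are 0.7 × 9 = 6.3 and 0.7 × 4 = 2.8 courses. If they are the three newest, 9 − 7 = 2 and 4 − 4 = 0 remain. Eight of the 9 courses, and all 4, fall after the first scan in week 7 or 8. If a fraction f then stops for progression (assumed), 0.7 × (1 + 8(1 − f)) or 0.7 × 4(1 − f) remain:

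- f = 25%: 4.9 courses (4-week review) or 2.1 (8-week review)
- f = 50%: 3.5 or 1.4
- f = 75%: 2.1 or 0.7

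**5. What raises it.** Section 4.3.2 says "slot enrollment will be used for the first 20 patient in each arm" to allow the early safety look, but does not state a full stop after patient 10. If enrolment continued, patients 11 onward would add 1 patient and 3 to 4 courses at 4 weeks, or 3 patients and 8 to 10 courses at 8 weeks, before dropout. The ranges reflect the two week conventions.

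**6. Colorectal Arm B.** At 1.5 patients per arm per month (one every 2.9 weeks) and the two-cycle review in 13.6, the first 10 have 2 patients and 3 courses outstanding, or 3 patients and 4 courses, depending on the week convention.

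**The case against.** The strongest reply is that this is silence, not contradiction. The Arm B sentence in 5.1 is a scheduling note that distinguishes four courses from one; it does not tell sites to carry on after a toxicity finding. A reader might infer that 5.1 and 13.6 directly conflict, and the documents do not go that far. What stands is that 5.1 is the default, and nothing displaces it at arm level.

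A reader might also infer that low-dose patients get no data review except after colorectal futility. That is not so: the trigger is itself the product of a full adverse event review of the first 10 low-dose patients. Only the further step is missing for Arm B.

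Nor is it right that the 33% pause can never help. With four of 10, or three DLTs plus one other severe event, it could be met if cohort means arm, and 13.6 does use the word for a group of 10. But 13.8.1 frames the pause as following a successful early assessment, which this would not be.

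Other controls exist. The treating radiation oncologist must consider the lesion safe to irradiate (5.1), the principal investigator reviews adverse events continuously (12.1), and the sponsor can terminate. These allow someone to act but do not say what happens to the arm.

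Finally, those of the first 10 without a DLT have cleared the 4-week DLT window, and the rule fires by chance fairly often (0.18 at a true rate of 15%). Both points favour a hold pending review over automatic cessation. They do not remove the need for a decision, because that window contains only the first of the four courses.

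**Conclusion.** The point holds as a gap in the arm-level safety rule, mainly for NSCLC Arm B: added RT is judged too toxic, enrolment stops, and the fate of courses already scheduled is left to patient-level holds, investigator judgment and general oversight. The 33% pause may help but is not met at exactly 3 of 10 on DLTs alone.

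The size is modest. Among the first 10, at most about 5 patients and 9 courses (4-week review) or 3 patients and 4 courses (8-week review) are outstanding before dropout. These figures rest on even accrual, treatment starting at registration and an immediate review. Data lag and dropout reduce them, possibly to none; continued enrolment during the review would add to them. The difference in review timing between 5.2 and 13.6 changes the counts but not the conclusion. Arm A is unaffected unless a hold has delayed its single course. This is a cheap improvement to a safety rule and not a flaw in the trial's inference.

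**What to change.** In 5.2 and 13.6, state that when the 3-of-10 rule is met in either RT arm:

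- all safety data from that arm are reviewed, removing the restriction to the high-dose arm;
- outstanding protocol RT for patients on that arm is held until the review decides whether RT continues;
- courses held under this rule are omitted if the review has not cleared them by the end of cycle 4, so that the postponement rule in Section 6 does not carry them forward;
- an arm-level RT hold or stop does not by itself trigger the Section 6 off-treatment provision.

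Apply the same to colorectal Arm B when its enrolment stops for toxicity.

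The cost is a few sentences in 5.2, 13.6 and Section 6, with no new data collection. The downside is a short delay or loss of a few 2 Gy palliative courses, sometimes after a chance trigger. Eligibility already excludes lesions that need urgent palliation.

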13.7 Analysis of Primary Endpoints

NSCLC: The proportion of patients with response (CR or PR according to RECIST) will be compared for each pair-wise comparison of RT-containing therapy and control using chi-squared tests. The difference between the proportions responding will be presented with a 90% confidence interval.

Colorectal Cancer: Response rates within each two-stage design will be calculated and presented with one-sided 90% confidence intervals estimated using the method of Atkinson and Brown, which allows for the two-stage design.

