13.3 Randomization

13.3.1 NSCLC

Patients enrolled in the NSCLC cohort will be randomly assigned in equal proportions to therapy with MEDI4736(durvalumab)/tremelimumab alone, MEDI4736(durvalumab)/tremelimumab with low-dose RT, or MEDI4736(durvalumab)/tremelimumab with high-dose RT. Forty patients will be assigned to each of the three therapies (120 in total).

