13.4 Sample Size/Accrual

13.4.1 Sample Size

NSCLC: Best overall response rate is the endpoint on which the sample size for cohort 1 is based. We estimate an overall response rate of approximately 5% for the combination of MEDI4736 and tremelimumab alone based on a comparison of preliminary response rates from patients treated with dual checkpoint blockade of PD-1 and CTLA-4 (Hellman et al. ASCO 2016) as compared with PD-1 inhibitor monotherapy [6]. Two, pair-wise comparisons of therapy with high- or low-dose radiation against the control of MEDI4736(durvalumab)/tremelimumab alone will be conducted. Since a positive outcome for each comparison in this trial is the superiority of MEDI4736(durvalumab)/tremelimumab with high- or low-dose RT compared with MEDI4736(durvalumab)/tremelimumab alone, we propose one-sided chi-squared tests for the null hypothesis of equality of the response rates with a 10% type-I error for each comparison. To assess for early evidence of futility or superiority of MEDI4736(durvalumab)/tremelimumab plus RT, each pairwise comparison will be based on a group sequential design with O'Brien-Fleming stopping boundaries for superiority and Gamma family boundaries ($\gamma=1$) for futility.

When the total sample size in each comparison is 80 patients (40 per arm), a chi-squared test will have 81% power to detect a difference between a 5% response rate and 22% response rate. Interim and final analyses will be conducted after 40 and 80 patients have objective response classifications (corresponding to 50% and 100% of the total information). The critical values $z_{SEP}^{[1]}$ of the test statistic for superiority of MEDI4736(durvalumab)/tremelimumab with RT in each comparison for the interim and final analyses would be 2.054 and 1.317, corresponding to nominal significance $z_{SEP}^{[1]}$ levels of 0.02 and 0.094, respectively. If the p-value at the interim analysis is greater than 0.463 (i.e., the test statistic is less than 0.0922), there will be insufficient evidence to reject $z_{SEP}^{[1]}$ the null hypothesis and the trial for that comparison (and enrollment to the respective RT arm)

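### The NSCLC response difference is given a 90% interval with no allowance for the interim stopping rule, so after an early superiority stop the reported effect would be too large

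*Combined protocol and SAP*

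**What the plan says.** Section 13.4.1 sets up two NSCLC comparisons, each of one radiotherapy arm against durvalumab/tremelimumab alone. Each is "based on a group sequential design with O'Brien-Fleming stopping boundaries for superiority", with a futility boundary as well. On the error rate: "we propose one-sided chi-squared tests for the null hypothesis of equality of the response rates with a 10% type-I error for each comparison". Looks are planned at 40 and 80 patients per comparison. The superiority critical values are 2.054 and 1.317, and the interim futility cut-off is 0.0922. On power: "a chi-squared test will have 81% power to detect a difference between a 5% response rate and 22% response rate".

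Section 13.7 covers the NSCLC estimate in one sentence: "The difference between the proportions responding will be presented with a 90% confidence interval". No method is named. The colorectal paragraph that follows uses the Atkinson and Brown interval, "which allows for the two-stage design". No other section supplies an NSCLC adjustment. Section 13.9.2 only asks in general terms for 95% intervals.

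**The concern.** A comparison stops early for superiority only when the interim difference is large. An ordinary estimate from those data is therefore selected to be high, and an ordinary interval around it is centred too high. Section 13.7 allows for this kind of selection in the colorectal interval but is silent for the randomised NSCLC comparisons. The natural reading of that silence is an ordinary difference with an ordinary interval.

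At stake is the size of effect the trial reports for adding radiation. After an early stop, readers would see a figure above the 17 points the design targets, whatever the true effect, with nothing in the planned analysis to temper it.

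**Working it through.** **Inputs (sections 13.3.1 and 13.4.1).** One-sided alpha 0.10 per comparison; 20 per arm at the interim and 40 at the end; z boundaries 2.054 and 1.317; futility below 0.0922; design rates 5% and 22%.

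**Reproducing the plan's design figures.**
- O'Brien-Fleming-type spending at half information: 2[1 − Φ(1.645/√0.5)] = 2[1 − Φ(2.326)] = 0.0200, so z = 2.054. This matches.
- Final boundary from the bivariate normal with correlation √0.5 and non-binding futility: 1.316, nominal level 0.094. This matches 1.317 and 0.094.
- Power at 5% versus 22%: 0.803 (pooled variance) or 0.822 (unpooled) by normal approximation, and 0.834 by exact enumeration. The plan states 81%.
- Stopping at the interim under the null: 0.537 for futility plus 0.020 for superiority gives 0.557. The plan states 0.56.

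**Smallest early win.** z = d / √[p̄(1 − p̄)(2/20)], with d the observed difference and p̄ the pooled rate.
- 4/20 versus 0/20: d = 0.20, p̄ = 0.10, z = 0.20/0.0949 = 2.11. Stops.
- 6/20 versus 1/20: d = 0.25, p̄ = 0.175, z = 0.25/0.1202 = 2.08. Stops.
- 8/20 versus 2/20: d = 0.30, z = 2.19. Stops.

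One response fewer in the radiotherapy arm fails the boundary in each case (z = 1.80, 1.77 and 1.89). Over all possible tables, the smallest difference that stops for superiority is 20 points.

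**Exact enumeration of the two-look rule** (binomial outcomes, 20 then 40 per arm; differences in points; coverage of unadjusted 90% intervals in %):

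| True rates | True diff. | P(early win) | Mean diff. given early win | Mean diff. overall | Wald / Newcombe overall | Wald / Newcombe given early win |
|---|---|---|---|---|---|---|
| 22% v 5% | 17 | 0.352 | 27.7 | 18.1 | 84.4 / 90.0 | 84 / 92 |
| 17% v 5% | 12 | 0.205 | 25.3 | 12.2 | 83.4 / 90.5 | 78 / 90 |
| 15% v 5% | 10 | 0.153 | 24.4 | 9.8 | 85.8 / 91.5 | 79 / 83 |
| 10% v 5% | 5 | 0.052 | 22.5 | 3.9 | 79.3 / 92.1 | 0 / 62 |

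With a fixed 40 per arm at 22% versus 5%, Wald covers 88.7% and Newcombe 90.8%. The sequential rule thus costs about 4 points of overall coverage for Wald (88.7 − 84.4) and about 1 for Newcombe (90.8 − 90.0).

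**What adjustment does to one early win, 6/20 versus 1/20 (raw difference 25 points).** The unpooled standard error is √(0.05 × 0.95/20 + 0.30 × 0.70/20) = 0.1135.
- Wald 90%: 25 ± 1.645 × 11.35, or 6.3 to 43.7.
- Repeated interval with 2.054: 25 ± 2.054 × 11.35, or 1.7 to 48.3. The point estimate does not move.
- Sample-mean ordering: median-unbiased estimate 22.1, 90% interval 4.9 to 37.7. This is a normal model with the pooled standard error; the ordinary interval with that standard error is 5.2 to 44.8.
- Bias-adjusted (Whitehead) estimate: 23.1.
- Stage-wise ordering: for a superiority stop at the first look, the more extreme outcomes are exactly the larger first-look values. The calculation reduces to the ordinary one, so estimate and interval are unchanged.

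**The case against.** Much of the case on the other side stands.

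- **Silence is not a choice.** A reader might infer that the plan prescribes a fixed-sample interval. It does not; it names no method. An unadjusted interval is the likely reading only because an adjustment is named for colorectal alone.
- **The inflation is conditional.** A reader might infer that the NSCLC estimate is badly biased in general. Averaged over all outcomes it is 18.1 against 17. Among all wins at the design alternative the mean is 21.3, but a fixed 40-per-arm test at one-sided 0.10 already gives 18.9 among wins. The sequential rule adds about 2.4 points (21.3 − 18.9); the rest is ordinary selection on significance.
- **Poor coverage is partly a Wald problem.** At 22% and 17% versus 5%, an unadjusted Newcombe interval holds about 90% overall and 92% and 90% given an early win. It falls short given an early win when the true effect is smaller (83% at 15% versus 5%).
- **The 27.7 assumes data frozen at 20 per arm.** Section 13.2.1 counts all randomised patients. If accrual ran on during response assessment, say 7 more per arm (an assumption), the mean after an early win would be (20 × 27.7 + 7 × 17)/27 = 24.9. Slot enrolment (section 4.3.2) may limit such overrun.
- **Later use.** A reader might infer that the inflated figure would size a phase 3 trial. The documents describe no such use.

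None of this removes the gap: the primary effect estimate has no stated allowance for a stopping rule that the plan itself sets.

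**Conclusion.** The concern holds as a matter of estimation and reporting. The boundaries 2.054 and 1.317 already protect the test, so the documents do not support a claim of excess false positives or a wrong decision.

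The effect is confined to early superiority stops. There the reported difference is at least 20 points, averaging 27.7 when the truth is 17 and 24.4 when it is 10. Such stops occur in about 35% and 15% of comparisons respectively. Coverage given an early win at 15% versus 5% is 79% (Wald) and 83% (Newcombe).

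These figures assume a 5% control rate, exactly 20 per arm at the interim, the pooled chi-squared statistic, adherence to both boundaries, and an unadjusted estimate and interval where the plan is silent. The change is worth making because it is cheap and the same section already makes a comparable allowance for colorectal. That allowance covers the interval only; no adjusted colorectal point estimate is mentioned.

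**What to change.** In the NSCLC paragraph of section 13.7, before the interim analysis, state that:

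1. the raw difference will be shown with a score-type (for example Newcombe) 90% interval, not a Wald interval;
2. it will be accompanied by a bias-adjusted estimate, or a median-unbiased estimate under sample-mean ordering;
3. a 90% interval reflecting the section 13.4.1 boundaries will be given, either the matching sample-mean-ordering interval or a repeated confidence interval.

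Stage-wise ordering should not be used, since it changes nothing after a first-look stop. A repeated interval alone is also not enough, since it leaves the estimate where it was. If it is built directly from 2.054 and 1.317, each limit carries the one-sided 10% level. As a two-sided interval its guaranteed level over both looks is 1 − 2 × 0.10 = 80%. It should be labelled accordingly or recomputed at 5% per side, which makes it wider.

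The cost is a few sentences and a little programming. After an early stop the estimate will be slightly less favourable (about 22 to 23 points instead of 25 for 6/20 versus 1/20), or the interval wider if the repeated form is chosen.
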